## 3.2 General study level definitions

### 3.2.1 Relative day

Relative day for an event will be derived with the date of the first administration of IMP as reference date.

Relative day for an event or measurement occurring before the reference date will be calculated as follows:

$$\text{Relative Day} = \text{Event Date} - \text{Reference Date}$$

The relative day for an event or measurement occurring on or after the reference date, up to the date of the last administration of IMP, will be calculated as follows:

$$\text{Relative Day} = (\text{Event Date} - \text{Reference Date}) + 1$$

For events or measurements occurring after the date of the last administration of IMP, relative day will be prefixed with '+' in the data listings and will be calculated as follows:

$$\text{Relative Day} = \text{Event Date} - \text{Date of Last Administration}$$

There is no relative Day 0. Relative day will not be calculated for partial dates in cases where relative day is shown in a subject data listing. In such cases, relative day should be presented as '-' in the subject data listings.

### 3.2.2 Study periods

For each subject completing the study, the maximum study duration will be 68 weeks and will comprise the following:

- Screening Period:  $\geq 2$  weeks with a maximum of 4 weeks prior to randomization
- Treatment Period: 12 weeks
- Treatment Extension Period: 36 weeks
- Safety Follow-Up Period: 20 weeks after the last dose of IMP (scheduled at Week 44, 4 weeks prior to the end of the Treatment Extension Period)

The end of the study is defined as the date of the last visit of the last subject in the study.

## 3.3 Definition of Baseline values

Baseline will be the last available value prior to the first administration of IMP. Scheduled or unscheduled measurements can be used as the Baseline value. Measurement-specific Baseline definitions (based on the schedule of assessments in the protocol) are presented in [Table 3-1](#).

**Table 3-1: Definition of Baseline**

Category	Measurement	Definition of Baseline
Efficacy	BASDAI	Visit 2 (Week 0); Screening result if missing at Week 0
	PGADA	Visit 2 (Week 0)

**Table 3–1: Definition of Baseline**

Category	Measurement	Definition of Baseline
	hs-CRP	Visit 2 (Week 0); Screening result if missing at Week 0
	PET-MRI/PET-CT	Visit 1 (Screening)
	BASFI	Visit 2 (Week 0); Screening if missing at Week 0
	Total and nocturnal spinal pain numeric rating scale (NRS)	Visit 2 (Week 0); Screening if missing at Week 0
	PhGADA	Visit 2 (Week 0)
	HADS	Visit 2 (Week 0); Screening if missing at Week 0
Safety	Vital signs	Visit 2 (Week 0); Screening if missing at Week 0
	12-lead ECG	Visit 2 (Week 0); Screening if missing at Week 0
	Clinical laboratory tests	Visit 2 (Week 0); Screening if missing at Week 0
	Body weight	Visit 1 (Screening)
	C-SSRS	Visit 2 (Week 0); Screening if missing at Week 0
Immunological	ADA	Visit 2 (Week 0)
Pharmacodynamic	Cytokines, chemokines, serum complement levels, mononuclear cell subtypes	Visit 2 (Week 0)

ADA=anti-drug antibody; BASDAI=Bath Ankylosing Spondylitis Disease Activity Index; BASFI=Bath Ankylosing Spondylitis Functional Index; C-SSRS=Columbia-Suicide Severity Rating Scale; ECG=electrocardiogram; HADS=Hospital Anxiety and Depression Scale; hs-CRP=high sensitivity C-reactive protein; PET-CT=positron-emission tomography-computed tomography; PET-MRI=positron-emission tomography-magnetic resonance imaging; PGADA=Patient's Global Assessment of Disease Activity; PhGADA=Physician's global assessment of disease activity.

The change from Baseline to any subsequent post-Baseline visit will be calculated as the simple difference between that post-Baseline visit's value and the Baseline value, as below:

$$\text{Post Baseline Visit Value} - \text{Baseline Visit Value}$$

The percentage change from Baseline to any subsequent post-Baseline visit will be calculated as follows:

$$100 \times (\text{Post Baseline Visit Value} - \text{Baseline Visit Value}) / (\text{Baseline Visit Value})$$

The same Baseline value will be used in the calculations of changes from Baseline and percentage changes from Baseline at all visits during the Treatment Period and Treatment Extension Period.

### **3.4 Protocol deviations**

Important protocol deviations (IPDs) are deviations from the protocol which potentially could have a meaningful impact on the primary objective of the study. The criteria for identifying such protocol deviations will be defined within the IPD document which is part of the data cleaning plan. Important protocol deviations will be classified according to the following categories:

- Inclusion/exclusion criteria deviations
- Administration of prohibited concomitant medications
- Deviations relating to withdrawal criteria
- Visit schedule deviations
- Study IMP administration deviations (including incorrect treatment received, handling and storage deviations and incorrect dosage received)
- Treatment non-compliance
- Procedural non-compliance
- Missing data
- Other

Important protocol deviations will be reviewed as part of the ongoing data cleaning process and data evaluation.

At least 4 data evaluation meetings (DEMs) will be performed at the following times, prior to each of the following analysis milestones:

- IA1
- IA2
- IA3
- The final analysis after all data have been verified/coded/entered into the database

Additional DEMs may be conducted as deemed necessary.

The purpose of these DEM reviews will be to review all protocol deviations, define the analysis sets as defined in [Section 3.5](#), and check the quality of the data. The reviews will also help decide how to manage problems in the subjects' data (eg, missing values and withdrawals).

Accepted deviations from theoretical (scheduled) time points will be described in the appropriate documents and included in the Study Master File. After the pre-analysis review, resolution of all issues, and documentation of all decisions (including inclusion into each of the analysis sets) at the final DEM, the database will be locked.

## **3.5 Analysis sets**

### **3.5.1 Enrolled Set**

The Enrolled Set (ES) will consist of all subjects who have given informed consent (ie, all subjects screened). The ES will therefore include screening failures.

### **3.5.2 Randomized Set**

The Randomized Set (RS) will consist of all randomized subjects.

### **3.5.3 Safety Set**

The Safety Set (SS) will consist of all randomized subjects who receive at least 1 dose (full or partial) of the IMP. The safety analysis will be conducted on the SS.

### **3.5.4 Full Analysis Set**

The Full Analysis Set (FAS) will consist of all randomized subjects who received at least 1 dose (full or partial) of the IMP and had a valid Baseline and a post-Baseline measurement for at least one efficacy variable (as defined in [Section 2.2.1](#)). The FAS will be used for the supportive and sensitivity analyses of the primary efficacy variable, the analyses of the secondary efficacy variables, other efficacy variables and the primary efficacy component data.

### **3.5.5 Per-Protocol Set**

The Per-Protocol Set (PPS) will consist of all subjects in the FAS who have no IPDs affecting the primary efficacy variable. The subjects with IPDs will be predefined and evaluated during a DEM prior to unblinding of the data. The PPS will be used for the primary analyses and supportive and sensitivity analyses of the primary efficacy variable, for the analysis of the component variables of the primary efficacy variable and for the analysis of the secondary efficacy variables.

Protocol deviations will be reviewed at the DEMs and any exclusions from analysis sets will be documented as described in [Section 3.4](#). It is anticipated that the PPS for the final analysis will differ from the PPS defined at the interim analyses due to additional information obtained on subjects during the SFU Period. Similarly, the PPS as defined at IA1, IA2 and IA3 may differ across the 3 IAs, due to potential additional data or information obtained during the time between each analysis.

Following the final DEM, the inclusion into each of the analysis sets for all subjects will be confirmed. The DEM minutes will document the final agreed PPS to be applied to the final analysis, as well as document any changes to the PPS relative to the previously agreed PPS at the interim(s), if applicable.

### **3.5.6 Pharmacokinetics Per-Protocol Set**

The Pharmacokinetics Per-Protocol Set (PK-PPS) will consist of all randomized subjects who receive at least 1 dose (full or partial) of the IMP and have at least 1 quantifiable post-dose plasma concentration. The summaries of the PK concentration data and the immunological data will be based on the PK-PPS.

### 3.5.7 Pharmacodynamics Per-Protocol Set

The Pharmacodynamics Per-Protocol Set (PD-PPS) is a subset of the FAS, consisting of those subjects who had no IPDs potentially affecting the PD data, as confirmed during a pre-analysis review of the data prior to database lock.

### 3.5.8 PET Per-Protocol Set

The PET Per-Protocol Set (PET-PPS) will consist of all randomized subjects who receive at least 1 dose of the IMP and have evaluable PET-MRI or PET-CT scan data at Baseline and at least 1 of the post-Baseline assessments.

## 3.6 Treatment assignment and treatment groups

Listings and summaries will be presented by treatment group and/or overall, as applicable ([Table 14-4](#)).

The following order will be used in the TFLs:

- Not randomized
- CZP
- BKZ
- All subjects

The dosing schedule and number of injections given at each visit for each treatment group are described in [Table 3-2](#).

The IMP will be administered in the clinic as 2 sc injections. Suitable areas for sc injection are the lateral abdominal wall, upper outer thigh, and upper arm. During each dosing visit, each of the 2 injections will be administered at a separate injection site.

In addition, subjects randomized to BKZ will receive 1 placebo injection at Baseline, Week 2, and Week 4 in order to maintain the blind vs the CZP loading dose at these visits.

The minimum time between doses should be no less than 10 days during the Treatment Period and no less than 22 days during the Treatment Extension Period.

**Table 3-2: Administration of investigational medicinal product**

Visit	Treatment group	
	Bimekizumab	Certolizumab Pegol
Treatment Period		
Baseline, Weeks 2, 4	160mg	400mg
Weeks 6, 8, 10	160mg	200mg
Treatment Extension Period		
Weeks 12 to 44, every 4 weeks	320mg	400mg

In the case of dosing administration errors during the Treatment Period, all statistical analyses of safety data will be conducted according to the actual treatment received, ie, treatment assignment for the SS will be based on actual treatment with the following rule:

- Subjects who received any doses of a treatment to which they were not randomized will be assessed at the DEM for the treatment group assignment, as it will depend on how many doses of each of the treatments were taken and at what time point during the study

Subjects receiving the incorrect treatment at a particular visit will be excluded from the PPS, PD-PPS and the PK-PPS as this would be considered as an IPD. Subjects may be excluded from the analysis at a particular visit (or visits) only or overall, following discussion at the DEMs, and will be included in the analyses according to their randomized treatment (which would be equivalent to an analysis according to their actual treatment).

All summaries of the PK and immunological data will be conducted according to the actual treatment received, ie, treatment assignment for the PK-PPS will be based on actual treatment.

Similarly, all statistical analyses of the PD data will be conducted according to the actual treatment received, ie, treatment assignment for the PD-PPS will be based on actual treatment.

### **3.7 Center pooling strategy**

Due to the small number of subjects per site, it is planned to pool all subjects within the study. The data summaries and statistical analyses will not be performed by site or country.

### **3.8 Coding dictionaries**

Adverse events and medical history will be coded using the Medical Dictionary for Regulatory Activities (MedDRA®) version 19.0.

Medications will be coded according to the World Health Organization Drug Dictionary (WHODD) version SEP2015. Medical procedures will not be coded.

### **3.9 Changes to protocol-defined analyses**

The following changes relative to the protocol-defined analyses have been included in the SAP:

- The PD-PPS was included as an additional analysis set in the SAP and was not part of the clinical study protocol. This was added as it was deemed appropriate to review protocol deviations separately in relation to the PD data and to define a separate analysis set accordingly.
- The HADS data are not included under the list of Other efficacy variables in the protocol. These data are, however, collected as supportive efficacy data and therefore the changes from Baseline in the total HADS-A and HADS-D scores are included in this SAP under [Section 2.2.1.3](#) for Other efficacy variables.
- The PhGADA data are not included under the list of Other efficacy variables in the protocol. These data are, however, collected as supportive efficacy data and therefore the change from Baseline in PhGADA is included in this SAP under [Section 2.2.1.3](#) for Other efficacy variables.
- The protocol defines the FAS as all randomized subjects who receive at least 1 dose of the IMP and have a valid measurement of the primary efficacy variable at Baseline and at least 1

post-Baseline efficacy assessment. The definition of the FAS in the SAP has been updated to include all randomized subjects who received at least 1 dose (full or partial) of the IMP and had a valid Baseline and a post-Baseline measurement for at least 1 efficacy variable. Since the primary efficacy variable is a composite endpoint based on BASDAI, PGADA and hs-CRP, the use of the protocol definition would omit any subjects with at least one missing component of the composite endpoint from the efficacy analyses.

## **4 STATISTICAL/ANALYTICAL ISSUES**

### **4.1 Adjustments for covariates**

The Bayesian analyses will employ a linear regression model adjusting for Baseline ASDAS as a covariate. Further exploratory analyses may be performed for the primary efficacy variable adjusting for other Baseline covariates.

### **4.2 Handling of dropouts or missing data**

#### **4.2.1 Efficacy data**

##### **4.2.1.1 ASDAS derivation**

If 1 component for the ASDAS is missing at a given visit, and the visit prior to the visit with the missing component data is not the Baseline or Screening visit, the following will apply: the missing component will be imputed by carrying the last observation for the given component forward, and the ASDAS will be calculated accordingly.

If no value is available for that component before the missing visit, or if the visit prior to the visit with the missing component data is either the Baseline or Screening visit, then the next observation will be carried backwards, and the ASDAS will be calculated accordingly.

If an unscheduled or repeat visit with non-missing data for the given ASDAS component is available and this visit is closer to the scheduled visit where the component data is missing, then the component data from the unscheduled/repeat visit will be used in the derivation of the ASDAS score.

If more than one component for the ASDAS is missing, ASDAS will not be calculated and treated as missing.

Any measurements of hs-CRP that are below 2 mg/L will be imputed with a fixed value of 2 mg/L for the purpose of deriving the ASDAS.

The statistical analysis will be performed based on the resulting derived values of ASDAS.

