5.7 Schedule of assessments

Table 5–1: Schedule of assessments

Study Period	SCR	Treatment Period								Treatment Extension Period								SFU ^a
Visit ^b /Week (Visit window ± 3 days)	V1	V2	V3	V4	V5	V6	V7	V8	V9	V10	V11	V12	V13	V14	V15	V16	V17	V18
Procedures	SV	BL W0	W2	W4	W6	W8	W10	W12	W16	W20	W24	W28	W32	W36	W40	W44	W48 /WD	W64
Written informed consent ^c	X																	
Demographic data	X																	
AS history	X																	
Inclusion/exclusion criteria	X	X ^d																
Significant past medical history and concomitant diseases	X	X ^e																
Prior and concomitant medications ^f	X	X	X	X	X	X	X	X	X	X	X	X	X	X	X	X	X	X
Adverse events	X	X	X	X	X	X	X	X	X	X	X	X	X	X	X	X	X	X
C-SSRS	X	X	X	X	X	X	X	X	X	X	X	X	X	X	X	X	X	X
HADS	X	X		X	X			X	X	X	X	X	X	X	X	X	X	X
BASDAI	X	X	X	X	X	X	X	X	X	X	X	X	X	X	X	X	X	X
BASFI	X	X	X	X	X	X	X	X	X	X	X	X	X	X	X	X	X	X
PGADA		X	X	X	X	X	X	X	X	X	X	X	X	X	X	X	X	X
PhGADA		X	X	X	X	X	X	X	X	X	X	X	X	X	X	X	X	X
Total and nocturnal spinal pain (NRS)	X	X	X	X	X	X	X	X	X	X	X	X	X	X	X	X	X	

Table 5–1: Schedule of assessments

Study Period	SCr	Treatment Period								Treatment Extension Period								SFU ^a
Visit ^b /Week (Visit window ± 3 days)	V1	V2	V3	V4	V5	V6	V7	V8	V9	V10	V11	V12	V13	V14	V15	V16	V17	V18
Procedures	SV	BL W0	W2	W4	W6	W8	W10	W12	W16	W20	W24	W28	W32	W36	W40	W44	W48 /WD	W64
Physical examination (incl. height and weight) ^g	X							X			X			X			X	
Vital signs (BP, pulse, temperature) ^h	X	X	X	X	X	X	X	X	X	X	X	X	X	X	X	X	X	
12-lead ECG (local)	X	X		X		X		X	X	X	X	X	X	X	X	X	X	
Tuberculosis questionnaire	X							X			X			X			X	
IGRA TB test ⁱ	X																X	
Pregnancy test ^j	X	X		X		X		X	X	X	X	X	X	X	X	X	X	
Hematology/biochemistry/urinalysis ^k	X	X	X	X	X	X	X	X			X			X			X	
Serology (HIV, Hepatitis B and C, HLA-B27) ^{k,l}	X																	
Blood samples for cytokines, complement, and biomarker analysis ^k		X		X				X			X			X			X	
Blood sampling for bimekizumab and CZP plasma concentrations ^k		X		X				X			X			X			X	
Bimekizumab and CZP antibody detection ^k		X		X				X			X			X			X	

Table 5–1: Schedule of assessments

Study Period	SCR	Treatment Period								Treatment Extension Period								SFU ^a
Visit ^b /Week (Visit window ± 3 days)	V1	V2	V3	V4	V5	V6	V7	V8	V9	V10	V11	V12	V13	V14	V15	V16	V17	V18
Procedures	SV	BL W0	W2	W4	W6	W8	W10	W12	W16	W20	W24	W28	W32	W36	W40	W44	W48 /WD	W64
Blood sample for hs-CRP ^k	X	X		X		X		X	X	X	X	X	X	X	X	X	X	X
Blood samples for pharmacogenetic variables		X						X									X	

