8.3 Week 2 (Visit 3)

The following procedures or assessments will be performed/recorded:

- Record concomitant medications.
- Assess adverse events.
- C-SSRS.
- Determine the BASDAI.
- Determine the BASFI.
- Perform the PGADA.
- Perform the PhGADA.
- Total and nocturnal spinal pain (NRS).
- Measure vital signs (temperature, pulse, and blood pressure).
- Collect samples for hematology/biochemistry/urinalysis.
- Administer IMP.
- Record visit in the IRT.

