12.6 Laboratory measurements

Clinical laboratory assessments consist of serum chemistry, hematology, and urinalysis, and pregnancy tests (serum or urine) (Table 12-2). A centralized laboratory will be used to supply all laboratory test supplies and analyze all blood and urine samples for hematology, biochemistry and urinalysis measurements. Any unscheduled laboratory testing should also be collected using

the central laboratory. Testing to rule out hepatitis B, hepatitis C, and HIV (see Exclusion Criterion #12, Section 6.2) will be performed at Screening in addition to those measurements listed in Table 12–2.

Specific details regarding the handling and processing of serum chemistry, hematology, and urinalysis samples are provided in the study laboratory manuals.

The following laboratory parameters will be measured:

Table 12–2: Laboratory measurements

Hematology	Chemistry	Urinalysis	Serology
Basophils	Bicarbonate	Albumin	HIV
Eosinophils	Calcium	Bacteria	HLA-B27
Lymphocytes	Chloride	Crystals	Hepatitis B
Atypical lymphocytes	hs-CRP ^a	Glucose	Hepatitis C
Monocytes	Magnesium	pH	
Neutrophils	Potassium	RBC	
Hematocrit	Sodium	WBC	
Hemoglobin	Glucose	Urine dipstick for pregnancy testing ^b	
MCH	BUN		
MCHC	Creatinine		
MCV	AST		
Platelet count	ALT		
RBC count	ALP		
WBC count	GGT		
	Total bilirubin ^c		
	LDH		
	Uric acid		
	Total cholesterol		
	Serum FSH testing ^d		
	Serum pregnancy testing ^b		

Table 12–2: Laboratory measurements

Hematology	Chemistry	Urinalysis	Serology
------------	-----------	------------	----------

ALP=alkaline phosphatase; ALT=alanine aminotransferase; AST=aspartate aminotransferase; BUN=blood urea nitrogen; FSH=follicle-stimulating hormone; GGT=gamma glutamyltransferase; HIV=human immunodeficiency virus; HLA-B27=human leukocyte antigen B27; hs-CRP=high sensitivity C-reactive protein; IMP=investigational medicinal product; LDH=lactate dehydrogenase; MCH=mean corpuscular hemoglobin; MCHC=mean corpuscular hemoglobin concentration; MCV=mean corpuscular volume; RBC=red blood cell; ULN=upper limit of normal; WBC=white blood cell

^a hs-CRP will be tested at specified visits per [Table 5–1](#).

^b A serum pregnancy test will be conducted at Screening – all other pregnancy tests will be performed on urine. Pregnancy results must be negative prior to administering IMP.

^c If total bilirubin is >ULN, a direct bilirubin estimation (%) will be performed.

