### 4.4 Handling of measurements obtained at the EW visit

Subjects withdrawing early from the study should undergo the same assessments scheduled for the Week 48 visit as soon as possible after withdrawal (as an EW visit) and then enter the SFU Period, completing study participation with the SFU Visit 20 weeks after their final dose of IMP.

The following rules will apply with regard to the inclusion of the results obtained at the EW visit in the descriptive summaries:

- Any measurements conducted at the EW visit should be included in the summaries for the respective scheduled visit, if the EW visit occurs at the time of the next scheduled visit. For example, if the EW visit occurs on Day 42, the results would be summarized together with the Visit 6 (Week 6, Day 42) results
- If the EW visit does not correspond to the day of a scheduled visit, the assessments of the EW visit should be mapped to the nearest scheduled visit, relative to the Baseline visit date, following the last scheduled visit where assessments are available
- If the date of the EW visit is equidistant between 2 scheduled visits at which no scheduled assessments were performed, the assessments from the EW visit will be mapped to the earliest of these visits
- If an EW visit mapping results in data being mapped to a visit where the specific assessment is not actually collected per the protocol schedule of assessments, these data will not be included in the summary statistics and will be listed only
- The only exception to the above rule is for ADA (for both BKZ and CZP) assessments, in which all early withdrawal visit assessments will be assigned to the next scheduled visit at which ADA are assessed. The rationale for this is that ADA positivity is summarized over a given study period. As part of that summary, a table indicating the first visit at which ADA positivity is observed will be presented. In order to match the number of subjects who were ADA positive at specific visits with the overall positivity for the period, it is necessary to ensure that ADA positivity is attributed to a visit where ADA antibody assessments were performed

Assessments from the EW visit will be displayed as the mapped visit and will be flagged in the by-visit data listings.

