#### **8.1.1.4 Calculation of Ankylosing Spondylitis Disease Activity Score**

Each of the individual component assessments described above in [Section 8.1.1.1](#), [Section 8.1.1.2](#) and [Section 8.1.1.3](#) are multiplied by a validated factor (van der Heijde et al, 2005) as listed below:

- 0.121 x Total spinal pain (BASDAI Question 2 result)
- 0.058 x Duration of morning stiffness (BASDAI Question 6 result)
- 0.110 x PGADA
- 0.073 x Peripheral pain/swelling (BASDAI Question 3 result)
- 0.579 x (natural logarithm of the hs-CRP [mg/L] + 1)

The results of these individual calculations or weighted components are then summed to obtain the ASDAS.

Handling of missing data and values of hs-CRP that are below 2 mg/L will be handled as described in [Section 4.2.1.1](#).

ASDAS will be calculated at Baseline and at each post-Baseline visit per the schedule of assessments in the protocol.

The primary efficacy analysis will be based on the change from Baseline in ASDAS at Week 12.

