### **8.1.6.4      Frequentist analysis – Mixed Model Repeated Measures**

A frequentist analysis of the change from Baseline in ASDAS will be performed using a MMRM. This model will use all available change from Baseline in ASDAS data at all post-Baseline visits during the Treatment Period up to and including Week 12. Treatment group (CZP and BKZ), visit, and the treatment group by visit interaction will be included as fixed effects and Baseline ASDAS will be included as a covariate.

An unstructured covariance matrix will be used to model the within-subject errors. If the model fails to converge, and/or if the estimated unstructured covariance matrix is not positive definite, then simpler alternative covariance structures will be considered (eg, compound symmetry).

Least squares means, SEs and associated 95% CIs for the changes from Baseline in ASDAS in each treatment group will be presented by visit. In addition, the estimated treatment difference in LSMeans (BKZ – CZP), SE, corresponding 95% CI, and p-value for the treatment comparison will be presented for each visit. Week 12 will be the primary time point of interest from this analysis.

The LSMeans for the changes from Baseline, including 95% CI, will be plotted versus time, with both treatment groups overlaid on the same axes.

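### The ASDAS fill rule is not limited to scheduled components, so read literally it builds ASDAS at Weeks 2, 6 and 10 from another visit's hs-CRP, and its Baseline exclusion can fail when a Week 4 hs-CRP is missing

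*SAP*

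**What the plan says.** **Schedule.** In Protocol Table 5-1 the row "Blood sample for hs-CRP" is marked at Screening, Baseline and Weeks 4, 8 and 12, and is blank at Weeks 2, 6 and 10. From Week 12 on it is marked at every visit, so the question concerns the Treatment Period only. BASDAI and PGADA are marked at all six post-Baseline visits to Week 12. The visit lists agree: at Week 2 (Protocol 8.3) the only blood and urine instruction is "Collect samples for hematology/biochemistry/urinalysis", and Weeks 6 and 10 (8.5, 8.7) are the same. Routine biochemistry does not supply hs-CRP, because a footnote to Table 12-2 states that "hs-CRP will be tested at specified visits per" Table 5-1.

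**Fill rule.** Under SAP 4.2.1.1, if one component is missing and the preceding visit is neither Baseline nor Screening, "the missing component will be imputed by carrying the last observation for the given component forward, and the ASDAS will be calculated accordingly". If the preceding visit is Baseline or Screening, or there is no earlier value, "then the next observation will be carried backwards". A closer unscheduled or repeat value takes precedence. ASDAS is left missing only when more than one component is missing. The section ends by basing the statistical analysis on the derived values.

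**Use.** SAP 8.1.1.4 says "ASDAS will be calculated at Baseline and at each post-Baseline visit per the schedule of assessments in the protocol". Of the MMRM, SAP 8.1.6.4 says "This model will use all available change from Baseline in ASDAS data at all post-Baseline visits" up to Week 12, and 8.1.6.5 repeats that model with an added interaction. The MMRM in 8.1.2.1 that predicts missing Week 12 values names no visits.

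**The concern.** At Weeks 2, 6 and 10 exactly one ASDAS component is absent for every subject by design, which is the condition that triggers the rule. A device for occasional gaps would then generate half of the post-Baseline ASDAS values to Week 12. At Week 2 it would use a measurement taken two weeks later.

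Three outputs are exposed: the by-visit ASDAS summaries, plots and disease-state tables; the two supportive MMRMs; and the supportive Bayesian analysis that uses predicted Week 12 values. In the prediction model the within-subject errors have a simple covariance structure. A subject who leaves after Week 6 would contribute one Week 4 CRP three times (Weeks 2, 4 and 6), as if in separate observations.

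The outputs would also disagree with each other. SAP 4.2.1.3 allows no imputation of missing values in the component summaries, so hs-CRP would be empty at Weeks 2, 6 and 10 while ASDAS was populated.

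A second gap lies in the exclusion of Baseline values. It looks at which visit came before, not at where the last observed component value came from.

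**Working it through.** The plan states no figure to reproduce. The check has two parts.

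**1. Apply the rule to the schedule.** The inputs are the Table 5-1 hs-CRP visits and the 4.2.1.1 rule, with no unscheduled samples and all other components present. Source of the CRP in each ASDAS:

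| Visit | All scheduled CRP present | Week 4 CRP missing | No post-Baseline CRP |
|---|---|---|---|
| Week 2 | Week 4 (back) | Week 8 (back) | none; ASDAS missing |
| Week 4 | own | Baseline (forward) | Baseline (forward) |
| Week 6 | Week 4 (forward) | Baseline (forward) | Baseline (forward) |
| Week 8 | own | own | Baseline (forward) |
| Week 10 | Week 8 (forward) | Week 8 (forward) | Baseline (forward) |
| Week 12 | own | own | Baseline (forward) |

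With complete scheduled data, 3 of 6 visits (50%) use another visit's CRP. When the Week 4 value is missing, the preceding visit is Week 2, so the Baseline exclusion does not apply. The last CRP observation is nevertheless the Baseline one, and it goes to Weeks 4 and 6. If only the Week 12 CRP is missing, Week 12 takes the Week 8 value.

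**2. Size of a misplaced CRP.** The CRP term in SAP 8.1.1.4, read as 0.579 × ln(CRP + 1) with values below 2 mg/L set to 2, gives

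shift = 0.579 × [ln(CRP used + 1) − ln(true CRP + 1)].

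The documents give no CRP values, so all of those below are assumptions.

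Week 2, with Week 4 CRP of 5 mg/L used:
- true Week 2 CRP 6: 0.579 × (ln 6 − ln 7) = −0.09
- true Week 2 CRP 8: 0.579 × (ln 6 − ln 9) = −0.24 (−0.235 before rounding)

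Week 4, with Baseline CRP used in place of a missing true value:
- Baseline 10, true 5: 0.579 × (ln 11 − ln 6) = 0.35
- Baseline 15, true 5: 0.579 × (ln 16 − ln 6) = 0.57
- Baseline 15, true 2: 0.579 × (ln 16 − ln 3) = 0.97
- Baseline 20, true 2: 0.579 × (ln 21 − ln 3) = 1.13

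These are shifts in one subject's ASDAS at one visit. No effect on a treatment difference was computed.

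**The case against.** The best defence is that the rule was never meant for unscheduled samples. SAP 8.1.1 describes ASDAS as built from component values of the same visit, 8.1.1.4 refers to the protocol schedule, and the rule sits in the section on dropouts and missing data, where a sample never planned need not count as missing. If ASDAS visits are simply the hs-CRP visits, the visit before Week 4 is Baseline, the exclusion works, and a missing Week 4 CRP takes the next value. Both problems then disappear.

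That reading is possible, but the text does not secure it. Table 5-1 has no ASDAS row, so the reference to the schedule does not say which visits count, and neither 4.2.1.1 nor 8.1.6.4 carries the limit. One reading gives a six-visit MMRM and the other a three-visit MMRM.

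It is also fair that the damage is bounded. The MMRMs are supportive. The model in 8.1.6.4 has treatment-by-visit effects, plans an unstructured covariance and makes Week 12 the time point of interest, so its Week 12 contrast rests mainly on observed Week 12 data. The same rule applies in both arms, so the contrast is biased only if CRP falls at different rates in the two arms. For that reason a within-subject shift should not be set against the planned between-group difference of 0.89.

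A reader might infer from SAP 4.4 that a real early-withdrawal CRP mapped to Week 6 or 10 is discarded while an older one is used, since "these data will not be included in the summary statistics and will be listed only". The documents do not show this. Section 4.4 governs descriptive summaries, 4.2.1.1 prefers a closer unscheduled value when deriving ASDAS, and 4.3 has unscheduled early-withdrawal measurements mapped and analysed.

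**Conclusion.** The point holds as a gap in the SAP wording. Read literally, 4.2.1.1 builds ASDAS at Weeks 2, 6 and 10 from Week 4, Week 4 and Week 8 CRP for every subject with those values. The results go to the by-visit summaries, the MMRMs in 8.1.6.4 and 8.1.6.5 and, because 8.1.2.1 sets no visit limit, the prediction model. On the assumed CRP values the Week 2 shift is about 0.09 to 0.24 units, in the direction of a lower Week 2 ASDAS.

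The Baseline exclusion also fails as written when a Week 4 CRP is missing. Baseline CRP then reaches Weeks 4 and 6 and adds about 0.35 to 1.13 units at Week 4 for that subject, again on assumed values.

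Two stronger readings are tempting and not supported. One is that Week 4 ASDAS routinely uses Baseline CRP. It does not: hs-CRP is drawn at Week 4, and Baseline is carried there only if that sample is missing. The other is that the primary result is compromised. The primary Bayesian analysis uses Week 12 only, excludes subjects with missing data, and hs-CRP is scheduled at Week 12. It is touched only if a Week 12 CRP is itself missing; Baseline CRP can reach Week 12 only if no post-Baseline CRP exists while the other Week 12 components do.

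**What to change.** Three changes to the SAP wording:

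- In 4.2.1.1, 8.1.2.1 and 8.1.6.4 (and so 8.1.6.5), state that ASDAS is derived and modelled only at visits where hs-CRP is scheduled, which in the Treatment Period are Weeks 4, 8 and 12.
- In 4.2.1.1, limit the carry-forward and carry-back rules to a component that was scheduled at that visit and is missing.
- Define the Baseline and Screening exclusion by the source of the last observed component value, not by the preceding visit. A missing Week 4 CRP would then take the next observed value, and a subject with no post-Baseline CRP would have no post-Baseline ASDAS.

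No new data are needed and the primary model does not change. The cost is that the supportive MMRMs and the prediction model use three visits instead of six, so patient-reported scores from Weeks 2, 6 and 10 no longer inform the ASDAS models. They remain in their own component summaries.
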